### **9.1.2 Sample Size**

The planned sample size for melanoma is up to 41 subjects with up to 24 subjects for Stage 1 and 17 subjects for Stage 2; the planned sample size for TNBC is up to 53 subjects with up to 24 subjects for Stage 1 and 29 subjects for Stage 2.

### **9.1.3 Efficacy Analyses**

Efficacy analysis will be conducted separately for each tumor type. The primary efficacy endpoint is ORR, and the secondary efficacy endpoints include PFS, TTR, CRR, DoR and OS. The primary efficacy population will include all evaluable subjects who receive at least one dose of study treatment, have measurable disease at baseline per RECIST v1.1, and have at least one post-baseline scan or discontinue study treatment as a result of progressive disease, death, or a treatment-related adverse event before the first post-baseline scan.

Hypotheses testing of ORR will be conducted among evaluable subjects at the dose which meets the safety criterion in Stage 1. Among the 12 evaluable subjects in Stage 1, at least 1 objective response in melanoma subjects would be needed to proceed to Stage 2 for melanoma; and at least 1 objective response in TNBC subjects would be needed to proceed to Stage 2 for TNBC. If there are at least 4 objective responses among the total of 29 evaluable subjects with melanoma and/or at least 5 objective responses among the total of 41 evaluable subjects with TNBC, the null hypothesis will be rejected for melanoma and/or TNBC and the study will be declared a success.

The point estimate along with the exact 95% confidence interval will be computed for ORR and CRR. PFS and OS will be summarized descriptively and graphically using the Kaplan-Meier method. The Kaplan-Meier estimate for the median, first, and third quartiles will be determined along with 95% confidence intervals (CIs). The Brookmeyer-Crowley method will be used for the CI calculations. For the subset of subjects who have a CR or PR, TTR and DoR will be summarized similarly using the Kaplan-Meier method. The Kaplan-Meier

estimate of PFS rate at the landmark times of 6 months and 1 year, and the OS rates at the landmark time of 1 year will be calculated.

Exploratory analyses may be conducted using iRECIST.

#### **9.1.4 Safety Analyses**

Safety analysis will be conducted separately for each tumor type. All subjects who receive at least 1 dose of study treatment will be included in the safety analysis. Adverse events by maximum toxicity grade will be summarized with frequency/proportion of total subjects by system organ class and preferred term. Separate summaries will be provided for all adverse events, drug-related adverse events, serious adverse events, and adverse events leading to discontinuation of study treatments. The incidence of deaths and the primary cause of death will be summarized. Hematology and clinical chemistry data will be summarized by worst-case toxicity grade shift from baseline. The results of other safety measurements (eg, ECOG performance status) will also be summarized.

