### 5.2.1.2.2 Pembrolizumab

Adverse events (both non-serious and serious) associated with pembrolizumab exposure may represent an immunologic etiology. These immune-related adverse events (irAEs) may occur shortly after the first dose or several months after the last dose of pembrolizumab treatment and may affect more than one body system simultaneously. Therefore, early recognition and initiation of treatment is critical to reduce complications. Based on existing clinical trial data, most irAEs were reversible and could be managed with interruptions of pembrolizumab, administration of corticosteroids, and/or other supportive care. For suspected irAEs, ensure adequate evaluation to confirm etiology or exclude other causes. Additional procedures or tests such as bronchoscopy, endoscopy, or skin biopsy may be included as part of the evaluation. Based on the severity of irAEs, withhold or permanently discontinue pembrolizumab and administer corticosteroids. Dose modification and toxicity management guidelines for irAEs associated with pembrolizumab are provided as per [Table 1](#) below.

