### **7.4.3 Every 2-Month Overall Survival Monitoring**

Upon completion of the 30-Day SFU visit, subjects will be monitored on an every 2-month visit schedule for survival until death or until study completion. Study completion is defined as the death of at least 70% of subjects or 3 years after the last subject's first dose, whichever occurs earlier.

Only survival status and start of any new anti-cancer therapy will be collected during this period.

Subjects who discontinue study drug without evidence of PD per RECIST v1.1 will have CT scans or MRI every 6 weeks during the survival-monitoring period to determine disease status until PD.

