Death due to any cause occurring >30 days after the last dose of study drug during the survival-monitoring period will not be reported as an adverse event. Disease progression will not be reported as an AE/SAE.

Each Investigator is responsible for reporting adverse events observed with concomitant medications per his/her region's respective regulatory guidelines.

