12.5 Deaths

All deaths will be summarized based on the number and percentage of subjects. This summary will classify subjects by time of death relative to the last dose of study treatment (>30 days or ≤ 30 days) and primary cause of death. A supportive listing will be generated to provide subject- specific details for subjects who died and the reason for death.

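### Cause of death is to be summarized for all deaths, but it is not among the items collected in survival follow-up, and the SAE route covers only some late deaths

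*Protocol*

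**What the plan says.** Two places plan an analysis of cause of death. Protocol 9.1.4 states "The incidence of deaths and the primary cause of death will be summarized", with no time limit. SAP 12.5 covers all deaths and classifies them by time "relative to the last dose of study treatment (>30 days or ≤ 30 days) and primary cause of death". It adds a listing with "specific details for subjects who died and the reason for death".

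Protocol 7.4.3 governs collection once treatment and the safety visit are over: "Upon completion of the 30-Day SFU visit, subjects will be monitored on an every 2-month visit schedule for survival". For that period it states "Only survival status and start of any new anti-cancer therapy will be collected during this period".

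Protocol 8.2.2 sets out SAE reporting in three steps:
- From enrollment to 90 days after treatment stops (30 days if new anticancer therapy starts), every death not due to progression is reportable, related or not.
- An SAE judged related is reportable at any time after that.
- A later paragraph says that a death "occurring >30 days after the last dose of study drug during the survival-monitoring period will not be reported as an adverse event".

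**The concern.** The analysis needs a variable that the collection rule leaves out. A site following 7.4.3 as written would record that a subject died, but not why. The more-than-30-day part of the SAP 12.5 summary would then have a stated source of cause only for deaths that reached the sponsor as SAEs.

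This matters because safety of the combination is a primary objective. Protocol 5.2.1.2.2 also says that immune-related events may occur "several months after the last dose of pembrolizumab treatment", so late deaths are the ones for which a recorded cause is most informative. If a late death produced no SAE report, the reader cannot tell whether it was due to progression, was unrelated, or was never assessed.

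**Working it through.** **The sections side by side**

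| Death occurs | Source of cause described in the documents |
|---|---|
| Day 31 to 90, not progression, no new therapy | SAE report under one paragraph of 8.2.2; not an adverse event under a later paragraph |
| Day 31 to 90, after new therapy has started | SAE report only if judged related |
| After day 90 | SAE report only if judged related |
| Any time after day 30, due to progression | None: progression deaths are outside SAE reporting, and 7.4.3 does not list cause |

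Relatedness is itself strict. Under Protocol 8.1.2, Yes requires that no other cause can be identified. In metastatic disease, progression is usually an available alternative, so an ambiguous late death need not be reported as related.

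**How many deaths this could involve**

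The documents give no figure for the timing of deaths, so there is none to reproduce. Inputs:
- Median OS 8.9 months and median PFS 2.0 months, from the phase 2 pembrolizumab monotherapy study in TNBC cited in Protocol 4.3.1.
- 41 TNBC subjects at the tested dose (Protocol 9.1.1).
- Completion at 70% of subjects dead (Protocol 7.4.3). Applying this to TNBC alone is an assumption, since the rule counts all subjects. It gives 0.70 × 41 = 28.7 deaths.
- Median time on drug m = 2, 3 or 4 months (assumed; 2 corresponds to stopping at progression).
- Independent exponential times and equal follow-up for all subjects (assumed).

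The death rate is λ = ln 2 / 8.9 = 0.0779 per month, so 70% are dead at τ = −ln(0.30)/λ = 15.46 months. The rate of stopping drug is μ = ln 2 / m. The gap is w = 30/30.4375 = 0.986 months, or 90/30.4375 = 2.957 months. The probability of dying before τ and more than w after stopping is

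P = [μ/(μ+λ)]·e^(−λw)·[1 − e^(−(μ+λ)(τ−w))] − e^(−λτ)·[1 − e^(−μ(τ−w))].

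The share of deaths is P/0.70 and the count is 41·P.

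| Gap | m | P | Share of deaths | Count of 28.7 |
|---|---|---|---|---|
| 30 days | 2 | 0.755 − 0.298 = 0.457 | 65% | 18.7 |
| 30 days | 3 | 0.685 − 0.289 = 0.395 | 56% | 16.2 |
| 30 days | 4 | 0.622 − 0.276 = 0.347 | 49.5% | 14.2 |
| 90 days | 2 | 0.645 − 0.296 = 0.349 | 50% | 14.3 |
| 90 days | 3 | 0.582 − 0.283 = 0.298 | 43% | 12.2 |
| 90 days | 4 | 0.524 − 0.266 = 0.259 | 37% | 10.6 |

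(Differences are taken before rounding.)

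**Sensitivity to the model**
- If every subject stops at exactly 2.0 months, the shares at 70% dead are 70% (about 20 of 29) beyond 30 days and 54% beyond 90 days. With OS at its lower confidence limit of 7.2 months they are 64% and 45%.
- If drug stops at progression, post-progression survival is calibrated to the 8.9-month median, and 0% to 20% of PFS events are deaths, the shares over 36 months are 72% to 88% beyond 30 days and 60% to 69% beyond 90 days.

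**The case against.** The strongest reply has three parts.

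First, the SAE rules are a real safeguard. A late death that the investigator judges drug-related is reportable without time limit, and SAP 12.3 lists fatal SAEs separately. A reader might infer that late toxic deaths cannot be told from progression at all. The documents do not support that. What can be missed is a toxic death that nobody recognized as related.

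Second, the word only in 7.4.3 is not applied literally even there: the same section requires scans every 6 weeks for subjects who stop drug without progression. The case report form is not in the documents, and the SAP points to some death data. SAP 12.5 lists the reason for death, SAP 10.1 summarizes end-of-study status, and SAP 6 mentions death data even for screen failures. A reader might infer that cause will be missing for most deaths. That is not established, because a death form may exist. None is described, however, and if it exists, 7.4.3 misstates what is collected and still needs correcting.

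Third, the size is easily overstated. With unlimited follow-up the same model gives μ/(μ+λ)·e^(−λw) = 76%, 69% and 64% beyond 30 days for m = 2, 3 and 4. Those shares cannot be applied to the first 70% of deaths, which over-represent early ones. At m = 4 the truncated share is just under half.

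All three parts limit the claim. None supplies a described source of cause for late deaths outside the SAE rules.

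**Conclusion.** The stated collection rule and the stated analysis contradict each other. Followed as written, the plan provides no systematic cause for deaths in survival follow-up, and the two paragraphs of 8.2.2 conflict for days 31 to 90.

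For TNBC, about 14 to 19 of roughly 29 deaths would fall more than 30 days after the last dose, and about 11 to 14 more than 90 days after. This rests on exponential times, a median time on drug of 2 to 4 months, equal follow-up, and 70% of 41 TNBC subjects having died; other reasonable models give higher shares. These are deaths falling in the affected period, not deaths certain to lack a cause, since some would be reported as SAEs. The documents give no melanoma PFS or OS benchmark for this setting, so no share can be stated for that cohort.

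The consequence is confined to a descriptive safety summary. ORR does not use cause of death, PFS and OS count death from any cause, and alpha and power are unchanged. The correction is still worth making because safety is a primary objective and cause becomes harder to obtain as time passes after a death.

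**What to change.** - Protocol 7.4.3: list survival status, date of death, primary cause of death (progression, study-treatment toxicity, other, unknown) and start of any new anti-cancer therapy.
- Protocol 8.2.2: reconcile the two paragraphs on reporting deaths between days 31 and 90, and check that SAP 12.3, which uses the 90-day SAE window, agrees with the result.
- SAP 12.5: add an unknown row and tabulate cause within each of the two time groups.
- If the item is not added, restrict the cause summary in Protocol 9.1.4 and SAP 12.5 to deaths within 30 days of the last dose, and say so.

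The cost is one case report form item at a two-monthly contact that already takes place (none if a death form already holds it), short edits to the protocol and one row in an SAP table. No visits are added and no design figure changes.

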#### **9.1.5 PK Analyses**

The PK analyses will be based on the PK population. The PK concentration data will be listed and summarized by planned visit/time.

#### **9.1.6 Interim Analyses**

One interim analysis will be conducted at the end of Stage 1 for each tumor type. For the dose which meets the safety criterion in Stage 1, if at least 1 objective response among 12 evaluable melanoma subjects is not observed, the melanoma cohort will be terminated; if at least 1 objective response among 12 TNBC evaluable subjects are not observed, the TNBC cohort will be terminated. Early stopping at the interim analysis will only occur for futility, not efficacy. Adverse events including  $\geq$  Grade 3 events will be summarized at the time of the interim analysis.

### **9.2 Statistical Analysis Plan**

A detailed Statistical Analysis Plan will be developed as a separate document for this protocol.

## **10.0 LABELING, PACKAGING, STORAGE AND RETURN OF CLINICAL SUPPLIES**

### **10.1 Investigational Product Identification and Description**

#### **10.1.1 Imprime PGG**

Imprime PGG will be provided by Biothera as a preservative-free, sterile, formulation in 20 or 50-mL clear borosilicate vials. Each vial will contain active ingredient at a nominal concentration of 1.0 mg/mL in 140 mM sodium chloride, 11 mM sodium citrate, at pH of 5.0 to 7.5. Vials are filled to a target volume of 21.2 or 52.0 mL respectively, to ensure a deliverable amount of 20 or 50 mL respectively. The active ingredient under investigation is  $\beta$ (1,6)-[poly-(1,3)-D-glucopyranosyl]-poly- $\beta$ (1,3)-D-glucopyranose (PGG beta glucan) derived from a proprietary, nonrecombinant strain of *Saccharomyces cerevisiae* and has an average molecular weight of 120,000 to 205,000 Daltons. The vehicle used to dilute Imprime PGG is 0.9% sodium chloride for injection. Each individual clinical study site will supply its own vehicle.

Imprime PGG will be individually labeled in accordance with local regulations. A label will be affixed to the vial with the following information.

Protocol: BT-CL-PGG-XXXXXXX Imprime PGG Injection (i.v.) 50mL (1mg/mL), Lot#:xxxxx Expiry: 50mg solution, dilute, infuse as directed Store at 20°C - 25°C- Do not freeze Biothera, [name] USA Caution: New drug- Limited by Federal (or United States) law to investigational use	Protocol: BT-CL-PGG-XXXXXXX Imprime PGG Injection 50mL (1mg/mL), Lot#:xxxxx Subject number: _____ Site/Investigator: _____ Date dispensed: _____ Dispensed by: _____ Biothera, [name] USA Investigator: _____
---	--

#### **10.1.2 Pembrolizumab**

For a complete description of pembrolizumab, please refer to the pembrolizumab regional prescribing guidelines (see [Appendix 14.2](#)).

In summary, pembrolizumab for injection is a sterile, preservative-free, white to off-white lyophilized powder in single-use vials. Each vial is reconstituted and diluted for intravenous infusion. Each 2 mL of reconstituted solution contains 50 mg of pembrolizumab and is formulated in L-histidine (3.1 mg), polysorbate 80 (0.4 mg), and sucrose (140 mg). It may contain hydrochloric acid/sodium hydroxide to adjust pH to 5.5.

Pembrolizumab will be provided by the Sponsor as summarized in [Table 5](#).

**Table 5. Pembrolizumab Product Description**

Product Name and Potency	Dosage Form
Pembrolizumab 50 mg	Lyophilized Powder for Injection
Pembrolizumab 100 mg/ 4mL	Solution for Injection

## **10.2 Storage and Handling of Clinical Study Material**

### **10.2.1 Storage and Handling of Imprime PGG**

Imprime PGG vials will be provided to the investigative site. Vials must be stored at controlled room temperature that encompasses the usual and customary working environment of 20°C - 25°C upon arrival at the site. A packing list will be included with the shipment of clinical study material. Upon receipt of study drug, the site will inspect the shipment for any damage, and compare contents against the packing list. The site will acknowledge receipt of the shipment and note any discrepancies or damages. Lot numbers and vial counts should be entered into the EDC.

### **10.2.2 Storage and Handling of Pembrolizumab**

Please refer to the pembrolizumab regional prescribing guidelines for a comprehensive discussion on the storage and handling of pembrolizumab (see [Appendix 14.2](#)).

## **10.3 Preparation, Dosing Instructions, and Schedule**

The clinical study site's pharmacist or the study Investigator will be responsible for the preparation of all study medications: Imprime PGG and pembrolizumab. All subjects will receive Imprime PGG prior to pembrolizumab. The compounds should be administered consecutively, at least 15 minutes apart (but no more than 30 minutes).

Instructions for the proper mixing and administration of Imprime PGG can be found in [Appendix 14.1](#) on [Imprime PGG Preparation and Dosing Instructions](#). A low protein binding 0.22-micrometer inline filter should be utilized during administration of Imprime PGG.

Instructions for the proper mixing and administration of pembrolizumab can be found in the regional prescribing guidelines for pembrolizumab.

Other drugs should not be added to the infusion mixtures, and IV lines should be flushed as per standard practice between infusions. Care should be taken to avoid extravasation at the infusion site. The infusion site should be monitored frequently for signs of inflammation.

The dosing schedule is presented in [Table 6.1](#) in the [Schedule of Assessments](#).

#### **10.4 Premedications**

Each cycle will be 3 weeks in duration. During this time, subjects may receive pre-treatment with standard anti-histamine medications before commencing dosing of study medications on each treatment day and, as needed, post-dose.

Premedications:

- Cycle 1/Day 1: Pretreat with an H1 antagonist (eg, 50 mg of diphenhydramine IV).
- Subsequent cycles: Premedication is allowed for each Imprime PGG infusion, but if tolerated by the subject, reduced premedication doses from those administered at Cycle 1/Day 1 should be used.

#### **10.5 Preparation and Dosing Instructions for Imprime PGG**

Refer to [Appendix 14.1](#) for complete instructions on the preparation and administration of Imprime PGG.

Imprime PGG is to be administered via IV infusion through a low protein binding 0.22-micrometer in-line filter; an infusion pump should be used to assure accurate and consistent dosing. Imprime PGG should not be administered as an intravenous push or bolus. [Table 6](#) below on Target Imprime PGG Administration Values describes recommended concentration, dilution volume, and administration time. Dependent upon actual total body weight on Cycle 1/Day 1, the concentration of the final diluted solution and the rate of infusion may be outside of the values in [Table 6](#), but should not exceed 0.8 mg/mL or 4.2 ml/min respectively. Site standard guidelines should be utilized for any re-calculations of study medication based on weight change.

**Table 6. Target Imprime PGG Administration Values**

Subject Weight (kg)	Dose Level (mg/kg)	Total Infusion Volume (mL)	Infusion Time (hours)	Rate of Infusion (mL/min)
≤75	4	500	2	4.2
>75 to ≤150	4	750	3	4.2
>150	4	1000	4	4.2
≤75	2	500	2	4.2
>75 to ≤150	2	750	3	4.2
>150	2	1000	4	4.2

**Note:** Concentration and rate calculations are based upon an average weight of 75 kg and are approximate; actual values will differ among subjects based upon total body weight and may therefore be outside of the ranges presented above in [Table 6](#).

Please refer to [Section 5.2.1.2.1](#) for instructions on handling infusion reactions related to the administration of Imprime PGG.

## 10.6 Preparation and Dosing Instructions for Pembrolizumab

Subjects will receive pembrolizumab at a dose of 200 mg IV on D1 of every 3-week cycle.

The lyophilized powder for pembrolizumab should be reconstituted and prepared per the pembrolizumab package insert (see [Appendix 14.2](#)).

Pembrolizumab should be administered on D1 of each 3-week cycle intravenously over 30 minutes.

Please refer to [Section 5.2.1.2.2](#) for instructions on handling infusion reactions related to the administration of pembrolizumab.

Please refer to the pembrolizumab regional prescribing guidelines for complete instructions on the preparation, storage, handling, administration, and toxicity of pembrolizumab.

## 11.0 CLINICAL STUDY ADMINISTRATION

This research will be carried out in accordance with ICH Guidelines, GCP, and with applicable local regulatory requirements. A subject's voluntary signing of the informed consent is a required precondition to participating in the study.

The Investigator is responsible for ensuring that the clinical study is conducted in accordance with the principles above, the protocol, and other applicable requirements of the governing regulatory body.

## **12.0 INFORMED CONSENT AND AUTHORIZATION FOR USE AND DISCLOSURE OF PROTECTED HEALTH INFORMATION**

Written informed consent, authorization of use, and disclosure of personal health information must be obtained from each subject (or the subject's legal representative) prior to performing any study-related procedures. Prior to signing the informed consent, the study must be thoroughly explained to the subject (or legal representative) and the subject must be given the opportunity to ask questions. Included in the explanation must be the aims and methods of the study, anticipated benefits, potential hazards, and any anticipated possible discomfort. It must be explained to the subjects that they are free not to participate in the study and that if they do decide to participate, they may elect to withdraw at anytime without prejudice to future care. Subjects will also be told of any available treatment alternatives.

Subjects will be told that competent authorities and authorized personnel may examine their records, but that their personal data will be kept strictly confidential and will not be made publicly available, nor will it be used for reasons other than those outlined in the informed consent. The subject's dated signature on the IRB/IEC-approved form constitutes consent. If a subject and/or his/her legal representative are unable to read, an impartial witness must be present during the entire informed consent discussion and the signature of the witness must be on the informed consent. The informed consent presented to the subject must be in his/her primary language and must have been IRB/IEC-approved.

One copy of the signed informed consent document and authorization will be given to the subject and the Investigator will retain another. The informed consent document and authorization, which is prepared by the Investigator, must have been reviewed and approved by the Sponsor, the Investigator's IRB/IEC, and privacy board, as applicable, prior to the initiation of the study. The consent document must contain the 20 elements of informed consent described in ICH E6 Section 4.8. The site shall document the informed consent process.

